### 5.0 Designs and methodology

**Study Design:** This will be a hybrid 1 study design (mixed methods), where we are testing effects of a clinical intervention on relevant outcomes while observing and gathering information on implementation. We propose a matched cluster randomized controlled trial (2 arms, 6 clusters/arm, n=75 participants per cluster), using mixed methods. We will enroll PMTCT clients at Kenyan health facilities offering either HITSystem 2.1 intervention or standard of care (SOC) services to evaluate the efficacy, implementation, and cost-effectiveness of HITSystem 2.1 to increase complete PMTCT retention and viral suppression. Participants will be enrolled in PMTCT and followed through 6 months postpartum, with focused data collection at enrollment, delivery, and 6 months postpartum, Figure 1.

**(a) Study sites:** Study sites will be located in Siaya, Mombasa, and Kilifi Counties. These counties were selected due to their (1) elevated MTCT rates and (2) lower density of interventions targeting MTCT that could confound the results of this evaluation. To be eligible for selection and matching in the study, health facilities must (1) provide PMTCT, EID, and ART services and (2) not be involved in any ongoing PMTCT or EID interventions or research studies.

We will collaborate closely with the national PMTCT technical working group to facilitate strategic site selection to maximize the similarity of facilities matched on geographic region, patient volume, and HIV prevalence. Finalized matches are outlined in Table 2.

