### **(b) Study Population**

The primary target population for the study is HIV-positive pregnant women.

**Inclusion criteria for HIV-positive pregnant women:** All HIV-positive women presenting for PMTCT services at study hospitals during pregnancy will be eligible for enrollment in the proposed study. Pregnant women under the age of 18 are eligible for inclusion in this study. Since Kenyan law allows pregnant women the same capacity to consent as an adult, young women under the age of 18 will be able to provide consent for themselves. Mentor mothers will take additional time with young women to ensure comprehension, emphasizing that participation is optional and not a requirement for receiving standard PMTCT/EID services for themselves or their infant.

Participants who do not own a mobile phone are also eligible for study enrollment. Investigators will not provide mobile phones to women but, rather, will evaluate the efficacy of the intervention's other components (alerts to provider for missed services) among participants without phones. Mobile phone ownership will be assessed as a mediator/moderator of intervention effectiveness.

**Exclusion criteria for HIV-positive pregnant women:** HIV-positive pregnant women will be excluded from study participation if she has any condition (including drug abuse, alcohol abuse, or psychiatric disorder) that study or hospital staff feel precludes her from providing informed consent. Capacity will be determined at the time of consent. Additionally, women who transfer care from one study site to another during their PMTCT services will be ineligible for enrollment at their new facility.

To assess mediators and moderators of HITSystem effectiveness, as well as part of the objective 4 evaluation of facility adoption, we will also interview providers at intervention and control hospitals.

**Inclusion criteria for providers:** Providers will be eligible to complete the survey if they (1) work primarily in ANC, PMTCT, CCC, laboratory, or MCH departments, (2) will have been involved in the provision of PMTCT care during the course of the study, and (3) have interacted with the HITSystem 2.1 during the course of the study (intervention sites, only).

**Exclusion criteria for providers:** Providers will be excluded from survey eligibility if they do not provide informed consent.

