### **(c) Sampling**

All HIV-positive pregnant women who present for care at study hospitals will be eligible for enrollment in the study. All eligible study candidates will be informed of the purpose of the research, including potential benefits and risks, prior to a request for written informed consent (Appendices 2A and 2B, see detailed informed consent section below). Women opting out of the study at intervention sites will have the option to either (1) access standard PMTCT services without enrollment in HITSystem 2.1, or (2) access HITSystem 2.1-supported PMTCT without their data being included in study analyses. Women opting out of the study at control sites will receive standard PMTCT services with their data being excluded from study analyses. Mentor mothers will document study enrollment and enrollment refusal at all sites.

Providers participating in interviews will be purposively sampled to represent a range of clinical departments and roles involved in the provision of PMTCT services.

**Sample size determination for Objective 1:** We estimated current levels of retention in complete, guideline-adherent PMTCT services based on findings from our R34 grant. Findings from our retrospective review at 4 Kenyan health facilities indicate only 50/424 (11.8%) of women enrolled in PMTCT received guideline adherent viral load testing. Based on average percentage point increases in complete retention achieved in previous studies (33% HITSytem 2.0 pilot [R34], 25% HITSytem 1.0 [R01]), we conservatively anticipate HITSytem 2.1 supported VL testing will exceed that of SOC by at least 20 percentage points (Table 3). We assume that the small subset of participants with guideline-adherent VL testing will be included among the larger population of those receiving complete PMTCT retention. To account for increased familiarity with guidelines over time and continually improving SOC, we assessed statistical power for contingencies with SOC guideline adherence as high as 18% using R package *clusterPower*. Assuming ICC=.05, the planned sample size of six 75-person clusters per arm provides 85% power to detect differences even smaller than the expected 20-percentage point difference across a range of possible SOC completion rates (Table 4). Using HITSytem 2.0 pilot data, we predict 28% attrition; thus, we need to enroll **n=96 women per cluster** (75 + 21).

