**Participant surveys:** A brief enrollment survey will collect same demographic and clinical data at control sites (without HITSystem 2.1) in addition to patient-level data regarding PMTCT information, motivation, partner status and support, HIV disclosure, depression (modified Edinburgh postnatal scale), and risk of violence (both arms, Appendix 2A). Repeated surveys after delivery and 6m postpartum (for VL sample collection described in Objective 2, both arms) will include these same patient-level measures to assess any changes that may mediate or moderate intervention impact (Appendices 2B & 2C). Participants will be compensated 200 KES for completion of each survey.

**Facility assessment form** (Appendix 2D) will be completed at the beginning, mid-point and end of study implementation to assess average resource level, annual PMTCT volume, and PMTCT provider-patient ratios.

**Provider surveys:** At baseline and again at the end of the study period, providers in both arms will be asked to complete a short survey (Appendix 2E) assessing provider role/ department, level of experience, knowledge and motivation regarding current PMTCT guidelines, and barriers and facilitators to provision of complete PMTCT services. We estimate n=5 providers per site to complete the survey for a total of n=60 providers (n=30 intervention, n=30 control). Prior to completing the survey, providers will complete an informed consent (Appendix 2C). Providers will be compensated 500 KES for completion of each survey.

**Supportive Supervision Visits** will occur monthly at all sites. During these visits, Site Coordinators will provide technical assistance and retraining, review study materials (informed consent forms, surveys), and review data for completeness and accuracy. The monthly frequency of site visits approximates programmatic HITSystem 1.0 implementation support in Kenya.

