**Effectiveness:** Objectives 1 & 2 assessing complete PMTCT retention and viral suppression will evaluate effectiveness. We will also measure adverse outcomes as a result of the program.

**Adoption:** At the *facility-level*, we will note any facilities which decline study participation and reasons for refusal. Among participating hospitals, the facility assessment form – filled out pre-mid-post study implementation – will collect data regarding resource level, patient-provider ratios, annual volume, implementing partners and outside support, and other facility details will be used to assess representativeness with Kenyan health care facilities. At the *provider-level*, adoption will be evaluated through provider surveys, assess the degree to which providers used HITSystem 2.1, determine which components were most beneficial, and assess facilitators and barriers to HITSystem 2.1 adoption. *Patient surveys* will similarly assess utility of SMS outreach components and suggestions to optimize benefit.

**Implementation:** Any changes to HITSystem 2.1 programming or study protocols will documented in research logs and/or through IRB amendments. Any changes to HITSystem 2.1 implementation at the hospital-level (i.e. location changes of desktop to better suit workflow, changes in key users, etc) will also be documented in study logs to guide implementation recommendations. We will review all HITSystem texting logs during the implementation period to assess fidelity of the SMS component by calculating the proportion of SMS sent according to participant preference (correct frequency and content) and the proportion received by a functioning mobile number. We will compare this with participants' reports of the number of SMS received as part of the study and the reasons for these SMS, which will be collected as part of the patient surveys.

**Maintenance:** Continued HITSystem 2.1 enrollment after the study enrollment period has ended (years 3-5) and utilization after the study follow up period (year 4-5) will serve as an indicator of system maintenance. In Years 3-5, the US-based study manager will compare the overall number of HITSystem 2.1 enrolments with PMTCT registers to assess if reach is being maintained. Using the HITSystem 2.1-generated alerts report, s/he will document the number and duration of provider alerts as a measure of system use.

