| 21. | Provider workload is too high to provide all recommended assessments for PMTCT.   |    |   |   |   |    |
| 22. | Guidelines are unclear and/or too complex to follow   |    |   |   |   |    |
| 23. | Mothers do not always consent and/or adhere to the guideline-adherent services that we provide  |    |   |   |   |    |
| 24. | Stock outs of supplies or drugs affect the provision of PMTCT services  |    |   |   |   |    |
| 25. | Patients are not adhering to PMTCT recommendations because they fear exposure to COVID-19.  |    |   |   |   |    |
| 26. | Hospital level protocol changes in response to COVID-19 (e.g. longer drug dispensing intervals, recommendations to limit patient exposure, etc) prevents me and my colleagues from providing PMTCT care as recommended by the national guidelines |    |   |   |   |    |

27. Please describe any other barriers to providing guideline-adherent PMTCT care \_\_\_\_\_

Interaction with HITSystem 2.1 (Intervention sites & End-of-Study, only)

28. On average, how many hours **per week** do you use the HITSystem?

- a. <1 hour
- b. 1-3 hours
- c. 3-5 hours
- d. 5-10 hours
- e. >10 hours

29. On average, how many days **per week** do you log in to the HITSystem?

- a. 1 days
- b. 2 days
- c. 3 days
- d. 4 days
- e. 5+ days

30. In the **past month**, have you logged into the HITSystem for any of the following reasons?

- a. To enter a new patient entry.....yes / no
- b. To update data on an existing patient entry.....yes / no
- c. To use alerts to identify patients who have missed services.....yes / no
- d. To check a patient's test result.....yes / no
- e. To find patient tracing information..... yes / no
- f. To access Kenya's national PMTCT/EID/VL guidelines.....yes / no
- g. To generate a report of review facility-level outcomes and data.....yes / no

31. Please rank each of the following HITSystem components by their level of usefulness to you, with 1 being the most useful and 5 being the least useful

- a. Patient tracking \_\_\_\_\_
- b. Accessing guidelines \_\_\_\_\_
- c. Generating reports \_\_\_\_\_
- d. Checking a lab result \_\_\_\_\_
- e. Locating a patient's clinical record \_\_\_\_\_

32. Briefly describe any challenges you experienced implementing HITSystem \_\_\_\_\_

---

---

---

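### Intervention-site staff who never used HITSystem 2.1 are ineligible for the only provider survey, so provider-level adoption barriers come from ever-users alone and the arm comparison is filtered on one side

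*Combined protocol and SAP*

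**What the plan says.** Section 5.0(b) sets three joint conditions for a provider to complete the survey: working mainly in one of the listed departments; criterion (2), that the provider "will have been involved in the provision of PMTCT care during the course of the study"; and criterion (3), that they "have interacted with the HITSystem 2.1 during the course of the study (intervention sites, only". Criteria (1) and (2) apply in both arms, and criterion (3) in one. Section 5.0(c) adds that providers are "purposively sampled to represent a range of clinical departments and roles".

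The Provider surveys paragraph under Procedures and Data Management fixes the timing: "At baseline and again at the end of the study period, providers in both arms will be asked to complete a short survey". It also fixes the number: "We estimate n=5 providers per site to complete the survey for a total of n=60 providers (n=30 intervention, n=30 control". Appendix IIE is the only provider instrument, and no separate eligibility rule is given for either round.

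Two analyses draw on it. Under Objective 3, in the Adoption paragraph, provider-level "adoption will be evaluated through provider surveys, assess the degree to which providers used HITSystem 2.1"; the same survey is to show which components helped most and what eased or hindered uptake. Under Objective 1, site averages of provider knowledge and motivation at baseline and end of study are compared over time and between arms as possible mediators. The last block of Appendix IIE (items 28 to 32) is headed "Interaction with HITSystem 2.1 (Intervention sites & End-of-Study, only".

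**The concern.** An assessment of why providers did or did not take up a system needs to hear from those who did not. Criterion (3) removes them before sampling starts. Staff who met the system and lapsed can still answer; staff who never engaged cannot, and their reasons are the ones a roll-out would most need.

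The filter is also one-sided. At end of study, knowledge and motivation scores at intervention sites come from staff selected for contact with the system, and those at control sites from staff selected only on department and involvement in PMTCT care. If people who engage with a new system tend to be better informed or more motivated, part of any difference between arms reflects selection. Finally, a rule that requires contact with the system sits badly with a survey round meant to precede the intervention.

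**Working it through.** **1. The plan's own figure.** The design is "2 arms, 6 clusters/arm, n=75 participants per cluster", so there are 2 × 6 = 12 sites. With 5 providers per site, 5 × 12 = 60 in total and 5 × 6 = 30 per arm. The stated 60 (30 + 30) reproduces. Two rounds give 60 × 2 = 120 planned forms. Objective 3 is declared unpowered, so no power formula applies.

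**2. Who can be reached at end of study.** Let q be the share of intervention-site staff meeting criteria (1) and (2) who never interacted with the system. The documents do not give q; 10% to 50% is my assumption. Under criterion (3) a never-user has zero chance of selection, so the expected number among 30 is 0 whatever q is. Without it, and if the sample roughly mirrors eligible staff, the number is 30 × q.

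| Assumed q | Never-users among 30, with criterion (3) | Without it (30 × q) |
|---|---|---|
| 10% | 0 | 3 |
| 20% | 0 | 6 |
| 30% | 0 | 9 |
| 50% | 0 | 15 |

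Never-users are plausible. The staffing paragraph makes the study's mentor mothers the main people entering data, and Section 8.0 restricts system access to research staff directly engaged in the study.

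**3. Effect on the comparison between arms.** Let d be the difference in mean score between users and never-users at an intervention site. The mean over all staff is (1 − q) × user mean + q × never-user mean. Surveying users only therefore shifts the site mean by q × d. With q from 10% to 50%, the shift is between one tenth and one half of d. Control sites have no corresponding shift. The documents give neither the size nor the sign of d.

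**4. The baseline round.** Objective 1 describes the provider measures as taken before and after the intervention. Taken literally, before launch 0 of 30 intervention providers satisfy criterion (3), while none of the 30 control providers is barred by it, leaving 120 − 30 = 90 feasible forms. But criterion (2) is written in the future perfect and equally cannot be confirmed at baseline, and the heading of the usage block presupposes an earlier round without it. The two places conflict as worded; a loss of 30 forms is not shown.

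**5. The form.** Item 29 (log-in days per week) starts at one day and has no zero. The lowest option of item 28 is under one hour, which can hold zero but does not separate a never-user from a light user. Every part of item 30 can be answered no, but it covers the past month only. Item 32 asks about challenges met while implementing the system. No item asks a never-user why.

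**The case against.** The strongest reply is that the damage is narrow. Objective 3 measures adoption at several levels. Facility refusals and facility forms, patient surveys, enrolment against paper registers, and the number and duration of alerts do not depend on criterion (3). At provider level the stated aim is degree of use, which items 28 to 31 still capture among ever-users. Contact with the system is a low bar and is not defined as logging in; a nurse who leaves data entry to the mentor mother may be following the intended workflow. Items 20 to 27, on barriers to guideline care, go to everyone surveyed in both arms. All of this stands.

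A reader might go further and infer that adoption will be overstated by the never-user share, since any use among eligible respondents is 100% by definition. The documents do not support that as a bias in a planned estimate: no section says an any-use proportion among providers will be reported. A reader might also infer that the whole adoption question is unanswerable, or that the intervention-arm baseline is lost. The separate data sources answer the first. The second rests on literal wording that the end-of-study label in Appendix IIE suggests was not intended.

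What the reply does not remove is that the plan sets out to identify barriers to uptake through this survey, and the survey excludes those who never took the system up. Counts of alerts or enrolments show low use, but not which staff never engaged or why. Purposive sampling by role cannot restore people who are ineligible.

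**Conclusion.** The point holds at provider level. As written, never-users contribute nothing to the assessment of adoption and its barriers, and the end-of-study comparison of provider knowledge and motivation sets ever-users against unselected control staff. The exclusion itself follows from the text without any assumption. Its size depends on q: about 3 to 15 of 30 respondents if q is 10% to 50%. The effect on the comparison between arms is q × d, with d unknown.

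The baseline conflict is a wording problem to be reconciled. Which rule was applied decides how the pre-post comparison reads: if baseline respondents were unselected and end-of-study respondents are users, part of the change at intervention sites may be a change in who was asked.

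The primary outcome comparisons do not depend on any of this. Objective 3 is descriptive and the provider scores serve mediation analyses, so this is worth correcting but does not threaten the trial's main conclusions.

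**What to change.** Delete criterion (3) as a survey eligibility rule, so that providers in both arms qualify on criteria (1) and (2) at both rounds, and keep purposive sampling by department and role. State for the baseline round that criterion (2) means expected involvement.

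Use HITSystem contact only as a skip rule for items 28 to 32 at end of study. Add never used to item 28 and zero days or never to item 29, and add one question asking never-users why they did not use the system.

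Report the numbers of users and never-users among intervention-site providers surveyed as a description of the sample. With about five purposively chosen providers per site, users divided by providers surveyed is not an adoption rate.

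Record which eligibility rule was applied at baseline. Two sites had already met their enrolment target when this version was written, so that round has probably passed. Section 7.0 places provider interviews in the year after enrolment stops, so the end-of-study round may still be correctable. In the same edit, Section 5.0(b) should assign the adoption evaluation to Objective 3, not Objective 4.

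The cost is one eligibility line, two response options and one question on a form used only in English; the planned 60 providers and their compensation do not change. The downside is that slightly fewer of the roughly five respondents per site will give component ratings.

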### **(c) Sampling**

All HIV-positive pregnant women who present for care at study hospitals will be eligible for enrollment in the study. All eligible study candidates will be informed of the purpose of the research, including potential benefits and risks, prior to a request for written informed consent (Appendices 2A and 2B, see detailed informed consent section below). Women opting out of the study at intervention sites will have the option to either (1) access standard PMTCT services without enrollment in HITSystem 2.1, or (2) access HITSystem 2.1-supported PMTCT without their data being included in study analyses. Women opting out of the study at control sites will receive standard PMTCT services with their data being excluded from study analyses. Mentor mothers will document study enrollment and enrollment refusal at all sites.

Providers participating in interviews will be purposively sampled to represent a range of clinical departments and roles involved in the provision of PMTCT services.

**Sample size determination for Objective 1:** We estimated current levels of retention in complete, guideline-adherent PMTCT services based on findings from our R34 grant. Findings from our retrospective review at 4 Kenyan health facilities indicate only 50/424 (11.8%) of women enrolled in PMTCT received guideline adherent viral load testing. Based on average percentage point increases in complete retention achieved in previous studies (33% HITSytem 2.0 pilot [R34], 25% HITSytem 1.0 [R01]), we conservatively anticipate HITSytem 2.1 supported VL testing will exceed that of SOC by at least 20 percentage points (Table 3). We assume that the small subset of participants with guideline-adherent VL testing will be included among the larger population of those receiving complete PMTCT retention. To account for increased familiarity with guidelines over time and continually improving SOC, we assessed statistical power for contingencies with SOC guideline adherence as high as 18% using R package *clusterPower*. Assuming ICC=.05, the planned sample size of six 75-person clusters per arm provides 85% power to detect differences even smaller than the expected 20-percentage point difference across a range of possible SOC completion rates (Table 4). Using HITSytem 2.0 pilot data, we predict 28% attrition; thus, we need to enroll **n=96 women per cluster** (75 + 21).

**Sample size considerations for Objective 2.** We draw upon limited pilot data, given the dearth of published data describing VL among women in pregnancy and in the postpartum periods, or estimates of VL of women who have disengaged from care in either period. Among PMTCT clients who received at least one VL test result, 31.3% of women in the control site had a detectable VL. Albeit small numbers, in the R34 intervention site which received intensified PMTCT retention support, but no prompts for VL testing or clinical action, 2/22 (9.1%) women had a detectable VL >1,000. These proportions reflect women engaged in clinical care during the study period. We estimate that women LTFU will have at least a 50% increased risk of a detectable VL given likely treatment interruption. In the control site, 24% of women were LTFU by the time of delivery, thus when averaging estimates for all women (retained and LTFU) we estimate 35% of women enrolled in SOC PMTCT will have a detectable VL compared to 10.2% (rounded up to 11%) in the HITSytem 2.1 sites (Table 5). With the strengthened VL component of HITSytem 2.1, we believe this estimate of 11% or less is realistic for the intervention arm. Using the R package *clusterPower*, we estimated power to detect a difference in proportions of detectable VL of .35 and .11. In an effort to demonstrate superiority of HITSytem 2.1 before accrual is complete, we will carry out an interim analysis after accruing 67% of the planned sample size in each arm. Splitting  $\alpha$  evenly between this interim analysis and the final analysis to preserve the overall  $\alpha$ -level at .05, power to detect the hypothesized .35 vs. .11 difference in the interim analysis at  $\alpha=.025$  is 95%. For a smaller difference of .30 vs. .11, power is 83% for the interim. Including the final analysis provides additional power. With the same estimates for attrition as detailed in Objective 1, the same number of participants are required for Objectives 1 & 2 (n= 75/cluster). However, a national stockout of viral load and infant HIV testing reagents caused a significant number of our sample to miss viral load and EID testing required for our aim 2 analyses. We have developed procedures to support postpartum VL testing and infant EID testing for the study (see below), however, prior to establishing these protocols, a total of 198 women and 320 infants missed routine testing due to this shortage. Two sites have already stopped enrolling, since they have met their required sample size of n=96 per site. We seek to add a total of n=30 participants to the ten sites that are still enrolling – for a total of n=300 participants across the study - to offset the statistical power lost due to missed testing from the national shortage. This would bring our total enrolled sample to n=1,452. We would enroll this sample for both aims 1 and 2, since both aims use the same patient population.

Given the clustered nature of the data, we analyzed power for tests of differences between proportions using the R package *clusterPower*, which uses simulation and generalized linear mixed modeling to estimate power for cluster-randomized trials, including those with a binary outcomes. Analyses for objectives 1 and 2 will use the same patient population; thus, no new participants will be enrolled for objective 2.

Objectives 3 will assess implementation outcomes and is not statistically powered. Women and providers included in surveys will be drawn from the existing study population, i.e. no new participants will be recruited for this objective.

Objective 4 does not require human subjects.

Table 3. Rates of guideline-adherent retention

|   | SOC               | HITSytem          |
|---|-------------------|-------------------|
| R01 HITSytem 1.0 cRCT
(complete retention - 18m pp) | 180/298,
(60%) | 334/474,
(85%) |
| R34 HITSytem 2.0 pilot
(complete retention - 7w pp) | 5/46,
(11%)    | 12/28,
(43%)   |
| PMTCT VL pilot data
(ANC and PP, per guideline)     | 50/424
(12%)   | (32%)*            |

\*Estimates 20 percentage point increase over SOC; pp=postpartum

Table 4. Differences detectable with 85% power, by SOC rate of complete PMTCT

| SOC rate | Minimum difference | Corresponding HITS rate |
|----------|--------------------|-------------------------|
| .08      | .16                | .24                     |
| .10      | .17                | .27                     |
| .12      | .18                | .30                     |
| .14      | .18                | .32                     |

Table 5. Estimated rates of detectable viral load

|   | SOC             | HITS 2.0/2.1   |
|---|-----------------|----------------|
| R34 pilot data                     |                 |                |
| Detectable VL result                      | 31.3%
(5/16) | 9.1%
(2/22) |
| Adjusted for LTFU*
50% increase | 35%             | 11%            |

\*LTFU estimated at 24%

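### Two sample-size inputs do not reproduce: 96 enrolled at 28% attrition leaves about 69 women per cluster, not 75, and Table 3's 334/474 is 70.5%, not 85%

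*Combined protocol and SAP*

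**What the plan says.** Section 5.0(c), sample size determination for Objective 1: "Assuming ICC=.05, the planned sample size of six 75-person clusters per arm provides 85% power to detect differences even smaller than" the expected 20-point difference. The enrolment target follows: "Using HITSytem 2.0 pilot data, we predict 28% attrition; thus, we need to enroll" "n=96 women per cluster", broken down as 75 + 21.

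The assumed effect is introduced with: "we conservatively anticipate HITSytem 2.1 supported VL testing will exceed that of SOC by at least 20 percentage points". Its support is the average of two earlier gains in complete retention: "33% HITSytem 2.0 pilot [R34], 25% HITSytem 1.0 [R01". Table 3 gives the counts behind them: 180/298 (60%) against 334/474 (85%) for HITSystem 1.0, and 5/46 (11%) against 12/28 (43%) for the HITSystem 2.0 pilot.

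The Objective 2 paragraph adopts the same attrition and the same 75 per cluster. It reports that two sites stopped enrolling on reaching 96, and adds 30 women at each of the other ten (total 1,452) to offset tests missed in a national reagent stockout. Section 7.0 builds the accrual plan on 96 per site.

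**The concern.** The 21 added to 75 is 28% of the women wanted at the end, whereas attrition acts on the women enrolled. The target therefore does not deliver the cluster size on which Table 4 and the Objective 2 power rest, and two sites closed on it.

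In Table 3, one printed percentage contradicts its own count. That row is one of only two results used to present a 20-point effect as conservative. If the counts are right, the larger of the two earlier studies gained half of the assumed effect.

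**Working it through.** **Attrition**

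Inputs from section 5.0(c): 75 evaluable per cluster, 6 clusters per arm, ICC .05, attrition 28%.

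- The plan's figure: 75 × (1 + 0.28) = 96.0. This reproduces 75 + 21.
- What 96 leaves: 96 × (1 − 0.28) = 69.1 per cluster. It would leave 75 only at attrition of 1 − 75/96 = 21.9%.
- What 75 needs: 75/(1 − 0.28) = 104.2, so 105.

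**Objective 1 power**

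Effective n per arm = 6m/[1 + (m − 1) × .05].

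- m = 75: 450/4.70 = 95.7.
- m = 69: 414/4.40 = 94.1.

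Power = Φ[(d − 1.96 × SE0)/SE1], with SE0 from the pooled proportion and SE1 from the two separate proportions. Two-sided .05 is assumed, because an alpha is stated only under Objective 2, and a normal approximation stands in for the plan's simulation. With m = 75 it reproduces Table 4:

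| SOC rate | Table 4 | m = 75 | m = 69 |
|---|---|---|---|
| .08 | .16 | .157 | .159 |
| .10 | .17 | .167 | .168 |
| .12 | .18 | .175 | .176 |
| .14 | .18 | .181 | .183 |

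At two decimals Table 4 does not change at 69. For .12 against .30, power is 87.0% at m = 75, 86.4% at 69 and 88.2% at 91.

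**Objective 2 power at the interim**

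The interim is at 67% of accrual with α = .025. The ICC is not restated there, so .05 is assumed. 67% of 75 is 50 per cluster, and 67% of 69 is 46.

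- Effective n per arm: 300/3.45 = 87.0 against 276/3.25 = 84.9.
- Power = Φ[d/√((p1q1 + p2q2)/n) − 2.241].
- .35 against .11: 95.4% falls to 94.9% (plan: 95%).
- .30 against .11: 82.9% falls to 82.0% (plan: 83%).

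**Amended enrolment**

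- Total: 10 × 126 + 2 × 96 = 1,452.
- Per site after attrition: 126 × 0.72 = 90.7 at ten sites, 69.1 at two.
- Overall: 1,452 × 0.72 = 1,045, against 12 × 75 = 900 planned.
- Removing first the 198 women reported as having missed routine testing: (1,452 − 198) × 0.72 = 903.

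**Table 3**

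- 180/298 = 60.4%, 5/46 = 10.9%, 12/28 = 42.9% and 50/424 = 11.8% all agree with print.
- 334/474 = 70.5%, against a printed 85%.
- HITSystem 1.0 gain: 70.5 − 60.4 = 10.1 points on the counts; 85 − 60 = 25 on the printed percentages.
- Mean earlier gain: (33 + 25)/2 = 29 as stated. From the counts, 42.9 − 10.9 = 32.0 for the pilot, so (32.0 + 10.1)/2 = 21.0.
- To give 85%, 334 would need a denominator of 391 to 395, or 474 a numerator of 401 to 405.

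**The case against.** The strongest reply is that neither slip changes the design, and most of that stands.

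**Power.** A reader might infer that the trial is underpowered or that planned enrolment misses its target. The documents do not support this. With six clusters per arm and ICC .05, a few women more or fewer per cluster barely move the effective n. The amended total exceeds 900 in aggregate, and is about 903 even after the 198 are removed first. A harsher bound takes all 198 off after attrition, 1,045 − 198 = 847, or about 71 per site on average. That still lies within the 69 to 75 range examined above, and some of these women may have a delivery or study-initiated test.

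**Denominator.** For Objective 1, a woman missing any service is coded 0, and only documented reasons such as transfer, pregnancy loss or death remove her. Undocumented loss stays in the analysis. The share of the 28% that is documented is not given, so at 96 enrolled the Objective 1 cluster size lies somewhere between 69 and 96 (power 86.4% to 88.4% for .12 against .30). The shortfall bears mainly on Objective 2, and even there active tracing, home sampling and study-initiated tests should recover some women.

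**Effect size.** A reader might infer that the Table 3 mismatch disproves the 20-point effect. It does not. The 25 points in the text agree with 85%, so a misprinted count is a live explanation. Even on the counts, the mean gain of 21 is still above 20, and Table 4 does not use 334/474.

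**SOC rate.** A reader might also argue that 12% is too high for a composite that includes viral load testing. The plan states a nesting assumption ("the small subset of participants with guideline-adherent VL testing will be included among the larger population of those receiving complete PMTCT retention") and allows the SOC rate to rise to 18%. The pilot's 5/46 comes from a different, small cohort with a 7-week window. A lower SOC rate also shrinks the detectable difference in Table 4, so this is not an error in the sizing.

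**Conclusion.** Both figures are wrong as printed, and the consequences are minor.

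The inflation uses the wrong form: 96 per cluster corresponds to about 69 evaluable at the stated attrition, and 75 would need 105. The cost is about 0.6 points of power for Objective 1 and 0.5 to 0.9 points at the Objective 2 interim. These sizes rest on a normal approximation, a two-sided test, and ICC .05 carried over to Objective 2. The extension was added for the stockout, not to repair the inflation. It more than covers the shortfall at ten sites before stockout losses, while the two closed sites stay at about 69. The documents do not say which arms those two sites belong to.

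The Table 3 inconsistency is certain, but its direction is not. If the percentage is right, the argument for 20 points stands. If the counts are right, 20 points is about the average of the earlier gains and twice that of the larger study, and cannot be called conservative. Only the sponsor, with the source trial in hand, can settle this.

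**What to change.** 1. In section 5.0(c), replace the inflation statement with the evaluable numbers expected under 28% attrition: about 69 at the two closed sites and about 91 at the ten extended sites, before stockout losses. Do not enrol more women for this.
2. Restate Table 4 and the Objective 2 power on those sizes, giving the ICC and alpha used for each. On the approximation above, Table 4 is unchanged to two decimals even at 69.
3. Add a sentence that for Objective 1 only documented-reason exclusions leave the denominator, so the shortfall bears mainly on Objective 2.
4. Reconcile 334/474 with the source trial. If the count is misprinted, correct it and leave the 25 points. If the counts are right, print 70%, change 25 points to 10, and stop describing the 20-point effect as conservative. The pilot gain should read 32 rather than 33 in either case.

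The cost is a text and table correction, a rerun of the existing power code, and a look at one source. Some stated figures become slightly less favourable. Design, enrolment and analysis are unaffected.
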